6.4 Per Protocol Set

Not applicable.

6.5 Patient-Reported Outcome (PRO) Analyses Set

The Patient-Reported Outcomes (PRO) Analysis Set will include all subjects in the SAS with a non-missing baseline and at least 1 non-missing post-baseline result for EORTC QLQ-C30. Subjects will be included in the analysis of each EORTC QLQ-C30 score for which they have non-missing data.

6.6 Pharmacokinetic/Pharmacodynamic Analyses Set

Not applicable.

7. Planned Analyses

7.1 Interim Analysis and Early Stopping Guidelines

Safety data will be reviewed on an ongoing basis. A data review team (DRT), internal to Amgen but external to the study team, will assess **safety after every fifth nonreplaceable subject has been dosed and given an opportunity to complete MDMP. Refer to Section 8.3 for details on replacement of subjects**. Based on their reviews, the DRT will make recommendations to Amgen regarding the continuation of the study. There will be no formal guidelines to stop for safety. The DRT will consist of 3 or more members including 2 or more clinicians with relevant specialties and 1 or more statisticians. The DRT will be supported by an independent statistician who is responsible for preparing reports that describe the ongoing clinical study data. If a DRT meeting and subsequent meetings occur around the same time, the DRT chair can decide to combine into one meeting. This request should be made to the independent statistician approximately 1 week before the DRT meeting and be documented in the meeting minutes. Details regarding the responsibilities of the DRT and the independent statistician will be described in the DRT Charter.

7.2 Primary Analysis

The primary analysis will occur when all subjects complete the end of study visit 30 days (\pm 3 days) after the last dose of up to 4 cycles of blinatumomab or withdraw from the study.

7.3 Final Analysis

The primary analysis will also be the final analysis.

8. Data Screening and Acceptance

8.1 General Principles

The objective of the data screening is to assess the quantity, quality, and statistical characteristics of the data relative to the requirements of the planned analyses.

The data base will be subjected to edit checks outlined in the data validation specification plan by Clinical data management (CDM) department. Any outstanding data issue will be communicated to CDM for resolution before the database lock.

8.2 Data Handling and Electronic Transfer of Data

The Amgen Global Study Operations-Data Management (GSO-DM) department will provide all data to be used in the planned analyses. This study will use the RAVE database.

Device data by Current Health will be provided to CDM in the agreed frequency.

8.3 Handling of Missing and Incomplete Data

In general, missing data will be treated as missing, unless stated otherwise. Missing response for questions in EORTC QLQ-C30 PRO will be imputed as defined in section 5 of this SAP.

The handling of incomplete and partial dates for adverse events and concomitant medications are described in Appendix D.

Subjects will be replaced for analysis if the outpatient monitoring during blinatumomab infusion is not established.

8.4 Detection of Bias

If applicable, the methods to detect bias are described in the analyses of particular endpoints.

8.5 Outliers

Any suspected outliers will be investigated by the study team and will be included in the database unless determined to be an error or there is supporting evidence or explanation to justify the exclusion. Any outliers excluded from the analysis will be discussed in the Clinical Study Report (CSR), including the reasons for exclusion and the impact of their exclusion on the study.

8.6 Distributional Characteristics

The statistical assumptions for analysis methods will be assessed. If the assumptions for the distributional characteristics are not met, these will be described, and further analyses may be carried out using data transformations or alternative analysis methods. The use of transformations or alternative analysis methods will be justified in the final study report.

8.7 Validation of Statistical Analyses

Programs will be developed and maintained and output will be verified in accordance with current risk-based quality control procedures.

Tables, figures, and listings will be produced with validated standard macro programs where standard macros can produce the specified outputs.

The production environment for statistical analyses consists of Amgen-supported versions of statistical analysis software; for example, the SAS System version 9.2 or later.

9. Statistical Methods of Analysis

9.1 General Considerations

Descriptive statistics for demographic and safety will be summarized as appropriate. For categorical variables, the number and percentage of subjects in each category will be summarized. Continuous variables will be summarized by n, mean, standard deviation, median, Q1 (25th percentile), Q3 (75th percentile), minimum, and maximum values.

9.2 Subject Accountability

The number and percent of subjects who were screened, enrolled, received at least one dose of Blinatumomab, completed MDMP period, completed study, along with the reasons for discontinuing protocol-specified therapy and discontinuing study will be summarized. The number and percent of subjects infused will be tabulated by study site. Key study dates for the first subject infused, last subject infused, and data cut-off date for analysis will be presented.

9.3 Important Protocol Deviations

Important Protocol Deviations (IPDs) categories are defined by the study team before the first subject's initial visit and updated during the IPD reviews throughout the study prior to database lock. These definitions of IPD categories, subcategory codes, and descriptions will be used during the course of the study. Eligibility deviations are defined in the protocol.

9.4 Demographic and Baseline Disease Characteristics

Demographic (i.e. age, age group [18 - 64, 65 - 74, 75 - 84, >=85], sex, race, and ethnicity) and baseline disease characteristics will be summarized using descriptive statistics for the Safety Analysis Set (SAS). If multiple races have been reported for a subject, the subject will be categorized as multiple race (as well as by combination of races).

The baseline characteristics to be summarized include:

- B-ALL Subtype
- MRD status following induction therapy (negative, positive)
- ECOG performance status (see Appendix C)
- Physical measurement (Height, Weight, BSA)
- Number of prior lines of therapy
- Prior anti-cancer treatment regimen

9.5 Efficacy Analyses

Not Applicable.

9.5.1 Analyses of Primary Efficacy Endpoint(s)

Not Applicable.

9.5.2 Analyses of Secondary Efficacy Endpoint(s)

Not Applicable.

9.5.3 Analyses of Exploratory Efficacy Endpoint(s) Not Applicable.

- 9.6 Safety Analyses
- 9.6.1 Analyses of Primary and Key Secondary Safety Endpoint(s)

Endpoint	Statistical Analysis Methods				
Primary	Subject incidence rate of primary endpoint (grade 3 or 4 CRS, NT or				
	any adverse event resulting in hospitalization during MDMP) will be				
	summarized and accompanied by 2-sided 95% exact binomial				
	confidence intervals (Clopper and Pearson, 1934). This endpoint will				
	be analyzed using PAS and repeated using interim analysis set.				
Кеу	TTI as defined in section 5 of SAP will be summarized as continuous variable with number of non-missing and valid TTI with mean, median, standard deviation, minimum and maximum.				
Secondary					
	Number and percent of subjects who had received at least one				
	therapeutic intervention (as defined in section 5 of SAP) will be				
	summarized in total and by types of intervention. Total number of				
	therapeutic interventions and type of therapeutic intervention will be				
	tabulated.				
	Number and percent of subjects with at least one alarm triggered will				
	be summarized in total and by reasons of alarm trigger. Total number				
	of alarms triggered and reasons for each alarm trigger (as specified				
	below) will be tabulated.				
	Technical				
	Patient message				
	Physiological – Axillary temperature				
	Physiological – Systolic blood pressure				
	Physiological – Spo2				
	Physiological – Respiratory rate				
	Physiological – Pulse rate				
	Descriptive statistics for number of alarms triggered and therapeutic				
	interventions received per person will also be presented.				
	This endpoint will be analyzed using PAS and repeated using interim analysis set.				

9.6.2 Adverse Events

The Medical Dictionary for Regulatory Activities (MedDRA) version 25.0 or later will be used to code all events to a system organ class (SOC) and a preferred term (PT). Severity will be coded by using CTCAE version 5.0 or later.

Subject incidence of all, serious, grade 3 and above, leading to withdrawal of investigational product, leading to interruption of investigational product, fatal, treatment-related, treatment-related serious, and treatment-related grade 3 and above TEAEs will be tabulated by SOC and PT in descending order of frequency. In addition, treatment-emergent adverse events will be summarized by SOC, PT, and grade; and by PT only in descending order of frequency.

Treatment-emergent events of interest (EOIs) will be summarized by EOI category and preferred term. In addition, for each EOI category, the subject incidence of all, serious, grade 3 and above, grade 4 and above, fatal, leading to withdrawal of IP, leading to interruption of IP will be summarized. Time to onset, duration, number of resolved events for select EOIs (infection, neurologic events and CRS) will also be summarized.

To support estimation of healthcare resource utilization associated with treatment-related AEs, the summary of subject incidence treatment related TEAEs will be provided for treatment related TEAEs that resulted in hospitalizations, treatment related TEAEs that resulted in surgeries, treatment related TEAEs that resulted in the use of concomitant medications, treatment related TEAEs that resulted in the use of device/procedure intervention (see SAP section 10 'Changes from Protocol-specified Analyses' for details on updates to endpoints of secondary objective for estimation of healthcare resource utilization).

The above analyses will be performed using subjects in the SAS.

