8.2.5.1.4 Reporting a Safety Endpoint as a Study Endpoint

Safety endpoints that are study endpoints are reported on the Events CRF. All endpoints that also meet the criteria of **serious adverse event** must also be transmitted to safety within 24 hours of the investigator's knowledge of the event (refer to Section 11.4).

- **8.2.5.2 Method of Detecting Adverse Events and Serious Adverse Events**Care will be taken not to introduce bias when detecting **adverse events** and/or **serious adverse events**. Open-ended and non-leading verbal questioning of the subject is the preferred method to inquire about **adverse event** occurrence.
- 8.2.5.3 Follow-up of Adverse Events and Serious Adverse Events

 After the initial adverse event/serious adverse event report, the investigator is required to proactively follow each event at subsequent visits/contacts. All adverse events and serious adverse events will be followed until resolution, stabilization, until the event is otherwise explained, or the subject is lost to follow-up (as defined in Section 7.2.2). Further information on follow-up procedures is given in Section 11.4.

All new information for previously reported **serious adverse events** must be sent to Amgen within 24 hours following **awareness** of the new information. If specifically requested, the investigator may need to provide additional follow-up information, such as discharge summaries, medical records, or extracts from the medical records. Information provided about the **serious adverse event** must be consistent with that recorded on the Event**s** CRF.

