of the investigator to review all documentation (eg, hospital progress notes,
laboratory, and diagnostics reports) related to the event.

Date: 21 April 2022 Page 87 of 108

- The investigator will then record all relevant adverse event/serious adverse event information in the Event case report form (CRF).
- The investigator must assign the following mandatory adverse event attributes:
 - Adverse event diagnosis or syndrome(s), if known (if not known, signs or symptoms);
 - Dates of onset and resolution (if resolved);
 - Did the event start prior to first dose of investigational product;
 - Assessment of seriousness;
 - Severity (or toxicity defined below);
 - Assessment of relatedness to IP [blinatumomab], or other protocol-required therapies or devices [Current Wearable Health Monitoring System (CWHMS)];
 - Action taken; and
 - Outcome of event.
- If the severity of an **adverse event** changes from the date of onset to the date of resolution, record a single event for each level of severity on the Event**s** CRF.
- It is not acceptable for the investigator to send photocopies of the subject's medical records to sponsor/responsible contact research organization in lieu of completion of the Events CRF page.
- If specifically requested, the investigator may need to provide additional follow-up
 information, such as discharge summaries, medical records, or extracts from the
 medical records. In this case, all subject identifiers, with the exception of the
 subject number, will be blinded on the copies of the medical records before
 submission to Amgen.
- The investigator will attempt to establish a diagnosis of the event based on signs, symptoms, and/or other clinical information. In such cases, the diagnosis (not the individual signs/symptoms) will be documented as the adverse event/serious adverse event.

Evaluating Adverse Events and Serious Adverse Events

Assessment of Severity

The investigator will make an assessment of severity for each **adverse event** and **serious adverse event** reported during the study. The assessment of severity will be based on:

The Common Terminology Criteria for Adverse Events, version 5.0 which is available at the following location:

http://ctep.cancer.gov/protocolDevelopment/electronic applications/ctc.htm.

Protocol Number: 20190014

Product: Blinatumomab
Protocol Number: 20190014

Date: 21 April 2022 Page 88 of 108

Assessment of Causality

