The protocol will provide instruction on what types of events to report for the study. This form is to be used ONLY to report events that must be captured in the Amgen safety database. *Indicates a mandatory field.

Types of Events to be reported on this form

Serious Adverse Events (regardless of causal relationship to IP)

1. Site Information

Site Number* – Enter your assigned site number for this study

Investigator*, Country*, Reporter*, Phone No., and Fax No. - Enter information requested

2. Subject Information

Subject ID Number* – Enter the entire number assigned to the subject

Age at event onset, Sex, and Race – Enter the subject's demographic information

End of Study date – If the subject has already completed the study or terminated the study early, enter the End of Study date

If you are submitting follow-up information to a previous report, provide the serious adverse event term for the previous report as well as the start date for the initial event.

3. Serious Adverse Event

Provide the date the Investigator became aware of this Information

Serious Adverse Event Diagnosis or Syndrome* –

- If the diagnosis is known, it should be entered. Do not list all signs/symptoms if they are included in the diagnosis.
- If a diagnosis is not known, the relevant signs/symptoms should be entered.
- If the event is fatal, the cause of death should be entered and autopsy results should be submitted, when available.

Date Started* – Enter date the adverse event first started (not the date on which the event met serious criteria) rather than the date of diagnosis or hospitalization. **This is a mandatory field.**

Date Ended – Enter date the adverse event ended and not the date when the event no longer met serious criteria. If the event has not ended at the time of the initial report, a follow-up report should be completed when the end date is known. If the event is fatal, enter the date of death as the end date.

If event occurred before the first dose of Investigational Product (IP)/drug under study, add a check mark in the corresponding box.

Is event serious?* - Indicate Yes or No. This is a mandatory field.

Serious Criteria Code* – This is a mandatory field for serious events. Enter all reasons why the reported event has met serious criteria:

- ➤ Immediately life-threatening Use only if the subject was at immediate risk of death from the event as it occurred. Emergency treatment is often required to sustain life in this situation.

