- > If the investigator decides an event should be reported in an expedited manner, but it does not meet other serious criteria, "Other Medically Important Serious Event" may be the appropriate serious criterion.

Relationship to IP – The Investigator must determine and enter the relationship of the event to the IP at the time the event is initially reported. **This is a mandatory field.**

Relationship to Amgen device* – The Investigator must determine and enter the relationship of the event to the Amgen device (eg, prefilled syringe, auto-injector) at the time the event is initially reported. If the study involves an Amgen device, this is a mandatory field. This question does not apply to non-Amgen devices used in the study (eg, heating pads, infusion pumps)

Outcome of Event* – Enter the code for the outcome of the event at the time the form is completed. This is a mandatory field.

- Resolved End date is known
- Not resolved / Unknown End date is unknown
- Fatal Event led to death

If event is related to a study procedure, such as a biopsy, radiotherapy or withdrawal of a current drug treatment during a wash-out period, add a check mark to the corresponding box. This does not include relationship to IP or concomitant medication – only diagnostic tests or activities mandated by the

Date: 21 April 2022 Page 91 of 108

protocol.

4. Hospitalization

If the subject was hospitalized, enter admission and discharge dates. Hospitalization is any in-patient hospital admission for medical reasons, including an overnight stay in a healthcare facility, regardless of duration. A pre-existing condition that did not worsen while on study which involved a hospitalization for an elective treatment, is not considered an adverse event. Protocol specified hospitalizations are exempt.

At the top of Page 2, provide your Site Number and the Subject ID Number in the designated section.

5. IP Administration including Lot # and Serial # when known / available.

Blinded or open-label – If applicable, indicate whether the investigational product is blinded or open-label

Initial Start Date - Enter date the product was first administered, regardless of dose.

Date of Dose Prior to or at the time of the Event – Enter date the product was last administered prior to, or at the time of, the onset of the event.

Dose, Route, and Frequency at or prior to the event – Enter the appropriate information for the dose, route and frequency at, or prior to, the onset of the event.

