Appendix C Eastern Cooperative Oncology Group Performance Status (ECOG PS) Scale

ECOG PS Scale						
Grade	Descriptions					
0	Fully active, able to carry on all pre-disease performance without restriction.					
1	Restricted in physically strenuous activity, but ambulatory and able to carry out work of a light or sedentary nature (eg, light housework, office work).					
2	Ambulatory and capable of all selfcare, but unable to carry out any work activities. Up and about more than 50% of waking hours.					
3	Capable of only limited selfcare, confined to bed or chair more than 50% of waking hours.					
4	Completely disabled. Cannot carry on any selfcare. Totally confined to bed or chair.					
5	Dead					

Source: Oken et al, 1982.

Appendix D Handling of Dates, Incomplete Dates and Missing Dates for Adverse Events and Concomitant Medications The following data will be imputed using the following algorithm:

- Adverse Events
- Concomitant Medications

		Stop Date							
		Complete: yyyymmdd		Partial: yyyymm		Partial: уууу			
Start Date		< 1 st dose	≥ 1 st dose	< 1 st dose yyyymm	≥ 1 st dose yyyymm	< 1 st dose yyyy	≥ 1 st dose yyyy	missing	
Partial: yyyymm	= 1st dose yyyymm	2	1	2	1	n/a	1	1	
	≠ 1 st dose yyyymm		2		2	2	2	2	
Partial: yyyy	= 1 st dose yyyy	3	1	3	1	n/a	1	1	
	≠ 1 st dose yyyy		3		3	3	3	3	
Missing		4	1	4	1	4	1	1	

Table 14-D-1. Imputation Rules for Partial or Missing Start Dates

1 = Impute the date of first dose

2 = Impute the first of the month

3 = Impute January 1 of the year

4 = Impute January 1 of the stop year

Note: If the start date imputation leads to a start date that is after the stop date, then do not impute the start date.

Imputation rules for partial or missing stop dates:

Initial imputation

- For partial stop date mmyyyy, impute the last of the month.
- For partial stop date yyyy, impute December 31 of the year.
- For completely missing stop date, do not impute.
- If the stop date imputation leads to a stop date that is after the death date, then impute the stop date as the death date.
- If the stop date imputation leads to a stop date that is before the start date, then there is a data error and do not impute the stop date. (ie. set the stop date as missing).

Imputation rules for partial or missing death dates:

- If death year and month are available but day is missing:

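### SAP 9.6.2 summarises duration of infections, neurologic events and CRS without a rule for events still ongoing, so the figure tends to be too short

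*SAP*

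**What the plan says.** SAP 9.6.2 commits to this for three groups of events of interest: "Time to onset, duration, number of resolved events for select EOIs (infection, neurologic events and CRS) will also be summarized". It gives no formula, no rule for ongoing events and no grade limit. SAP Section 5 defines duration of therapy but not duration of an event.

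The other rules that bear on it are:

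- **Data collection.** Protocol Section 11.4 lists the attributes an investigator must record on the Events CRF, among them "Dates of onset and resolution (if resolved").
- **Missing stop dates.** SAP Appendix D: "For completely missing stop date, do not impute".
- **Missing data generally.** SAP 8.3: "In general, missing data will be treated as missing, unless stated otherwise".
- **Statistics.** SAP 9.1 summarises continuous variables by n, mean, standard deviation, median, quartiles and range.
- **Length of follow-up.** Under protocol 8.2.5.3, events "will be followed until resolution, stabilization, until the event is otherwise explained, or the subject is lost to follow-up", so follow-up can stop without resolution.
- **SAE contingency form.** The instructions in protocol Figure 11-1 give the unresolved outcome as "Not resolved / Unknown End date is unknown" and say of deaths: "If the event is fatal, enter the date of death as the end date".

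The only censoring method in either document is in protocol 9.4.2.3.1: Kaplan-Meier, as an option for time to therapeutic intervention.

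**The concern.** A duration needs a start and a stop. If only resolved events have a stop, the summary describes the events that ended while someone was watching. Whether an event is included then depends on the quantity being measured, because a long event has more chance of outlasting follow-up. The error leans toward reassurance.

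Ongoing events are foreseeable here. The end-of-study visit falls about 30 days after the last dose, and protocol 8.1.4 brings it forward when new treatment starts, including transplant conditioning. The study schema allows transplant at any time.

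At stake is a supporting description of CRS and neurotoxicity under fully outpatient dosing. The primary endpoint is not affected.

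**Working it through.** **Plan's own figure.** The documents give no figure for event duration. The one computed design figure, the 53.5% expected upper limit, reproduces: the Clopper-Pearson limit averaged over Binomial(45, 0.38) is 53.52%. It has no bearing on this point.

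**Step 1: follow one ongoing event through the rules.**
1. It is not resolved, so the Events CRF asks for no resolution date (protocol 11.4).
2. The stop date is completely missing, so it is not imputed (SAP Appendix D).
3. Missing stays missing (SAP 8.3).
4. Stop minus start cannot be computed, and SAP 9.1 offers only ordinary statistics on non-missing values.
5. The event contributes no duration.

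**Step 2: bounds on the effect.** Let u be the share of events without a stop date; the documents do not give it.

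- *Lower bound.* If non-resolution is unrelated to duration, the remaining events are a random sample and the bias is 0 at any u.
- *Worst case.* If the missing events are exactly the longest share u, the median of the rest is the true (1−u)/2 quantile. For exponential durations:

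  reported/true = ln((1+u)/2) / ln(1/2) = 1 − ln(1+u)/ln 2

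  At u = 5% this is 1 − 0.0488/0.6931 = 0.930. For a Weibull with shape k, raise the ratio to the power 1/k.

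| u | Exponential | Weibull, k = 0.7 | Weibull, k = 1.5 |
|---|---|---|---|
| 5% | 7.0% too short | 9.9% | 4.7% |
| 10% | 13.8% | 19.0% | 9.4% |
| 20% | 26.3% | 35.3% | 18.4% |

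**Step 3: a less extreme mechanism.** Assume exponential durations, an observation window uniform on 0 to F days, and only events that end inside the window summarised (2 million simulated events). All values are assumed.

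| True median (days) | F (days) | Without stop date | Observed median (days) | Too short by | Worst case at same u |
|---|---|---|---|---|---|
| 5 ln 2 = 3.47 | 72 | 7.0% | 3.22 | 1 − 3.22/3.47 = 7% | ln 1.070/ln 2 = 10% |
| 3.47 | 30 | 16.6% | 2.86 | 18% | 22% |
| 10 ln 2 = 6.93 | 72 | 13.9% | 5.93 | 14% | 19% |
| 6.93 | 30 | 31.7% | 4.58 | 34% | 40% |

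The direction is the same throughout, and each result lies between zero and the worst case.

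**Step 4: a small made-up example.** Six events resolve at 2, 3, 4, 5, 6 and 8 days, two are ongoing at 30 and 45 days, and one subject dies at day 2.

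- Resolved events only: median (4+5)/2 = 4.5 days.
- Death also counted as an end: the values 2, 2, 3, 4, 5, 6, 8 have median 4.0 days.
- Time to resolution with ongoing events censored and the death never resolving: the unresolved proportion is 5/9 after day 5 and 4/9 after day 6, so the median is 6.0 days. Censoring the death instead also gives 6.0.

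**The case against.** Several points on the other side stand.

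- **Non-resolution is not hidden.** The sentence that promises duration also promises the number of resolved events, and SAP 9.6.2 tabulates fatal events by category. A reader can see that events are missing. The duration figure is still not corrected.
- **Appendix D is not at fault.** Leaving a wholly missing stop date missing is what a censored analysis needs. The gap is that SAP 9.6.2 does not say what happens next; an unpublished table specification might.
- **The longest events need not be the ones lost.** A reader might infer that they always are. An unresolved event may simply have begun shortly before last contact, so this is a tendency, and the Step 2 percentages are worst cases.
- **Deaths.** A reader might infer that fatal events definitely enter as short, completed durations. The documents do not establish this. The rule is in the instructions for the paper contingency form, which is used when the electronic system is unavailable and covers serious events only. The Events CRF asks for a resolution date only if the event resolved. In Appendix D, "then impute the stop date as the death date" applies only when an imputed stop date falls after death.
- **Scaling to severe neurotoxicity.** A reader might set one unresolved event against the roughly six subjects expected to have grade 3 or higher neurotoxicity (13% of 45 = 5.9). The summary has no grade limit, so that denominator is too small.
- **Importance.** Duration is not a named endpoint in SAP 2.1, protocol 9.4.2.3.2 does not mention it, and no hypothesis is tested.

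**Conclusion.** The point holds for unresolved events. With duration taken as stop minus start, the stated rules leave ongoing events out of the summary, and the result tends to be too short. The bias runs from 0 to, with exponential durations and the longest events lost, about 7% of the median at 5% unresolved, 14% at 10% and 26% at 20%. Heavier-tailed durations would raise the worst case and lighter-tailed ones would lower it. The unresolved share is unknown and may be small, given follow-up to resolution or stabilization.

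The fatal-event part is conditional: only if the Events CRF follows the contingency form's end-date convention would deaths count as completed durations.

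This is a minor matter of specification in a descriptive safety table.

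**What to change.** In SAP 9.6.2, define the measure for these three groups as time to resolution. Censor unresolved events at the end-of-study visit or last contact. Estimate by Kaplan-Meier, or by cumulative incidence of resolution with death as a competing event. Do not count fatal events as resolved.

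At minimum, keep the simple summary but label it *duration of resolved events*, exclude fatal events from it, and print the unresolved count beside it.

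The cost is SAP wording and one changed table. Event outcome and stop date are already collected, the end-of-study visit date is on its own CRF page, and Appendix D already derives the last contact date. The drawback is that, with few events or many unresolved, the median may not be estimable; the minimum version avoids that.
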